5.8. Safety Analyses

All safety analyses will be performed on the Safety Analysis Set. Missing data will be maintained as missing, unless otherwise specified. All safety analyses will be descriptive in nature.

5.8.1. Extent of Exposure

Duration of study drug exposure, defined as the number of days between the date of first dose following randomization and the date of the last dose, will be summarized by treatment group.

Duration will be calculated as date of last dose – date of first dose + 1.

In addition, the number and proportion of participants with study drug exposure of 0-3, 4, 5, 6, 7 and 8-10 days will be summarized by treatment group

5.8.2. Adverse Events

Adverse events will be coded using the Medical Dictionary for Regulatory Activities (MedDRA). All AEs that occur on or after the date of first dose of study intervention will be considered Treatment Emergent Adverse Events (TEAEs), and will be summarized using frequency counts and percentages, with the number of participants in the safety set used as the denominator.

Summaries of TEAEs will be presented by treatment group, and overall, using the MedDRA level hierarchy (system organ class and preferred term) as follows:

- Overall TEAEs (i.e., regardless of intensity or relationship to treatment)
- TEAEs by NCI CTCAE intensity grade (Grade 1, 2, 3, 4, 5)
- TEAEs by relationship to study medication (related, not related)
- TEAEs leading to permanent discontinuation of study medication (i.e., action taken is drug withdrawn)
- TEAEs leading to permanent discontinuation of study medication (i.e., action taken is drug withdrawn) by relationship to study medication
- Serious TEAEs (SAEs)
- SAEs by relationship to study medication (related, not related)

Unless otherwise specified, at each level of summarization a participant will be counted once if they reported one or more events at that level of summarization. If more than one occurrence of an event is reported, the event of the worst intensity or the worst-case relationship assessment will be summarized.

In the case of an incomplete AE start date, determining if an AE is treatment emergent will be based on the following rules. If the day is missing and the month and year of an onset date are provided and on or after the date of randomization, the following rules will be applied.

- If month/year of the onset date is on or after the month/year of randomization, the AE will be considered treatment emergent.
- If month/year of the onset date is equal to the month/year of randomization, and the end date is present, the end date will be used to determine when the AE started. If the end date is on or after randomization, the AE will be considered treatment emergent; otherwise, if the AE stopped before randomization, then it will not be considered treatment emergent.
- If month/year of the onset date is equal to the month/year of randomization, and the end date is a partial date, the AE will be considered treatment emergent.
- If, despite implementing the above conventions, the onset date of the AE cannot be placed before, on, or after randomization, then the event will be considered treatment emergent.

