6.6. Concomitant Therapy

All medications including over-the-counter medications and herbal supplements taken during the 30 days prior to the first study drug administration will be recorded and reviewed by the Investigator (or designee) to determine whether the subject is eligible for inclusion.

Treatment with another study drug, investigational device, or approved therapy for investigational use within 30 days (or five half-lives, whichever is longer) before anticipated dosing is prohibited.

Allowed medications during the study:

- Remdesivir

Note, for subjects receiving remdesivir therapy, BLD-2660 is to be administered at least an hour before remdesivir administration.

6.6.1. Prohibited Medications and Herbal Supplements:

Below is a list of medications that are prohibited **during the study**.

- Anti-IL-6, IL-6 receptor antagonists, or JAKi

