5.9.6. Concomitant Medications

Concomitant medications are those that are taken at any time after the first dose of study medication.

If the start day of a medication is missing, then if the month and year of the start date are on or after the date of randomization, the following rules will be applied:

- If month/year of the start date is equal or after the month/year of the date of randomization, the medication will be considered concomitant;
- If month/year of the start date is equal to the month/year of the date of randomization, and the end date is present, the end date will be used to determine if the medication stopped prior to randomization or after. If the end date is after, the medication will be considered concomitant; otherwise, if the medication stopped prior, then it will be considered to be prior;
- If month/year of the start date is equal to the month/year of the date of randomization, and the end date is a partial date, the medication will be considered concomitant;
- If, despite implementing the above conventions, the start date of the medication cannot be placed before, on, or after randomization, then the medication will be considered concomitant.

Concomitant medications will be coded using the World Health Organization (WHO) Drug Dictionary and summarized by drug class (ATC Level 3) and preferred term for each treatment group. The summaries will present the number and percentage of participants using each medication by treatment group and overall. Participants may have more than one medication per drug class or preferred term. At each level of summarization, a participant is counted once if he/she reported one or more medications at that level. No statistical hypothesis tests will be performed.

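### SAP 5.8.2 and 5.9.6: the first two partial-date rules overlap with no stated precedence, so a same-month record that ended before randomization gets two opposite labels

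*SAP*

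**What the plan says.** SAP 5.8.2 counts an adverse event as treatment-emergent from the day of first dose onward. For incomplete onset dates it gives four rules, introduced by the condition "If the day is missing and the month and year of an onset date are provided and on or after the date of randomization".

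- Rule 1: "If month/year of the onset date is on or after the month/year of randomization, the AE will be considered treatment emergent". It places no condition on the end date.
- Rule 2 opens "If month/year of the onset date is equal to the month/year of randomization, and the end date is present" and then decides by the end date. For an event already over it says: "otherwise, if the AE stopped before randomization, then it will not be considered treatment emergent".
- Rule 3 keeps the same month but "and the end date is a partial date, the AE will be considered treatment emergent".
- Rule 4 is a fallback: an event that still cannot be placed is treatment-emergent.

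SAP 5.9.6 defines a concomitant medication as one taken after first dose, then uses the same structure. Its first rule reads "If month/year of the start date is equal or after the month/year of the date of randomization, the medication will be considered concomitant". Its second sends a same-month medication that had already ended the other way: "otherwise, if the medication stopped prior, then it will be considered to be prior".

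Such records can occur. Protocol 8.3.1 collects events from consent and has those starting before study drug shown as non-TEAEs. Under Protocol 6.6, medications "taken during the 30 days prior to the first study drug administration will be recorded".

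**The concern.** The first rule includes the randomization month and the second rule is written only for that month, so the two share records. For one kind of record they disagree, and the SAP does not say that the rules run in order or that the specific rule overrides the general one. Two competent programmers could derive different flags from the same data, and neither could be shown wrong from the text.

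At stake are the TEAE tables, with TEAE incidence listed as a secondary endpoint in SAP 1.1, and the concomitant-medication tables. An event that resolved before any study drug could be counted as treatment-emergent. A short course completed before entry could be reported as taken on study.

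**Working it through.** No sample size, power or alpha figure is involved. The check is to list every kind of record the rules can meet and see which rules apply.

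**Step 1. Rule 1 against the entry condition.** With the day missing, the entry condition can only be read at month level: onset in the randomization month or later. Rule 1 asks for the same thing. As written, it therefore classifies every record that enters the list, and the other rules have no records of their own.

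**Step 2. Enumeration.** Start month (same or later) crossed with end date (before randomization, on or after it, partial, missing) gives 2 × 4 = 8 types. A later start month with an end before randomization is impossible, which leaves 7. TE means treatment-emergent; for medications read concomitant for TE and prior for not TE.

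| Start month | End date | Rules met as written | Conflict | With rule 1 limited to later months |
|---|---|---|---|---|
| Same | Before randomization | 1: TE; 2: not TE | **Yes** | 2: not TE |
| Same | On or after | 1: TE; 2: TE | No | 2: TE |
| Same | Partial | 1: TE; 3: TE | No | 3: TE |
| Same | Missing | 1: TE | No | 4: TE |
| Later | On or after | 1: TE | No | 1: TE |
| Later | Partial | 1: TE | No | 1: TE |
| Later | Missing | 1: TE | No | 1: TE |

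As written, rule 1 takes in 4 of the 4 same-month types, and 1 of the 7 types receives contradictory labels. With rule 1 limited to later months, each type meets exactly one rule and there are 0 conflicts. The medication list behaves the same way. One minor difference is that its second rule mentions an end date after or before randomization but not on the day itself.

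**Step 3. Order of application.** In listed order with the first match kept, the conflicting record is TE or concomitant. If the later, specific rule overrides, it is not TE or prior. The other 6 types get the same label either way.

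**Step 4. Room for affected records.** An affected record must start and end before randomization but in the same calendar month. Assume that randomization falls evenly on days k = 1 to 30 of a 30-day month.

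- Medications (30-day look-back, Protocol 6.6): the mean of (k − 1) is 435/30 = 14.5 days, about 48% of the look-back.
- Adverse events (screening up to 3 days, SAP 1.2): the mean of min(k − 1, 3) is (0 + 1 + 2 + 27 × 3)/30 = 84/30 = 2.8 days at most.

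The medication window is about five times as wide (14.5/2.8 ≈ 5.2). These are windows of opportunity, not counts of records.

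**The case against.** The strongest reply is that the SAP never says to stop at the first match. Rule 2 is the only rule that uses a known end date, so a sensible programmer lets it override. The closing rule in each list treats the preceding conventions as a set. The main definitions also exclude an item known to have ended before first dose. The SAP's introduction mentions a separate document that holds any example code, and it may settle the order.

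Much of this stands. A reader might infer that rule 2 can never operate and that such records will be mislabelled. That holds only under listed-order, first-match coding, which the documents do not prescribe. What does not fall away is that the text gives two answers and no means of choosing. The protocol's non-TEAE rule does not settle it either, because the SAP says that it prevails over the protocol where they differ.

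A reader might also infer that the error reaches the efficacy models, since corticosteroid and other drug-use variables appear in SAP 5.5.2, 5.6.2 and 5.7. The documents do not support this. Nothing says that those variables are built from the 5.9.6 flag, and the only use stated there is a summary without hypothesis tests.

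Lastly, the rules compare with randomization while the main definitions use first dose. Both are scheduled on Day 1 (Protocol 1.2), so at date level they normally coincide. This is a matter of consistency, with no demonstrated effect.

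**Conclusion.** The point holds as an internal contradiction in two derivation rules. In both SAP sections, a record with a missing start day, a start in the randomization month and a known end date before randomization is labelled one way by rule 1 and the opposite way by rule 2. Rule 1's label is the one that conflicts with the first-dose definitions and with Protocol 8.3.1. Rule 2 was evidently written for this case.

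The size is small. SAP 5.8 makes all safety analyses descriptive, and the medication tables carry no tests. No primary test is shown to be affected. For adverse events the effect is probably very small: the event must start and end within a screening period of at most 3 days and lack a start day but have an end date. For medications it is somewhat larger because of the 30-day look-back. Any overcount would follow the same rule in both arms.

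A count of affected records cannot be supported. It would need the number of completed prior courses per participant, the rate of missing start days and the share of those records with a complete end date. The documents give none of these.

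**What to change.** In SAP 5.8.2 and 5.9.6, limit the first rule to start months after the randomization month. The same-month rules then govern same-month records, and each record type meets one rule. For consistency, compare with the date of first dose throughout both lists, as the main definitions do. While the medication rule is being edited, say how an end date on the reference day itself is treated.

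The cost is a few words in two sections and a matching check of the two flag derivations, before database lock. No data collection changes.

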5.8.3. Safety Labs

This study will be using local labs instead of central labs. Descriptive summary statistics of the observed values and change from baseline values for hematology, chemistry and urinalysis data at screening, baseline and each post-baseline visit (i.e., Day 5/Discharge, Day 10/Discharge, 14, 21 and 28) will be presented by treatment group. Boxplots will be used to display the distribution of the observed values over time, by treatment group.

Participants with clinically significant values for any safety labs are to be reported as an AE and therefore clinically significant laboratory findings will be interpreted from the AE summaries.

A listing of participants with clinically significant drug-related troponin elevations that have repeat elevation upon confirmatory testing as adjudicated by the DMC while continuing study drug during the 10-day treatment period will be provided.

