Serum troponin		X	X	X	X	X	X		
D-dimer		X	Day 5	X	X	X	X		
Pharmacokinetics plasma*			Day 5						Predose and 1-2 hours postdose *if naso-gastic tube (NGT) is inserted, PK samples will also be collected 2 hours postdose after the first NGT use.

Procedure	Screening	Treatment Period			Follow-up			Post-study visit	Notes
		BL	Daily visits [‡]	EOT/ET*			EOS		
Study Day	-3 to -1	1	2-9	10	14	21	28	+60 days from EOS	Baseline (BL); End of Treatment (EOT), Early termination (ET); End of study (EOS) ‡ If a subject is discharged prior to Day 10, they will complete Day 5 and Day 10 visits assessments * This visit will be conducted at hospital discharge, if subject is discharged prior to Day 10
Visit window (days)				±1	±2	±2	±2	±10	
Serum Pregnancy test (WOCBP only)	X								Women of childbearing potential (WOCBP)
12-lead ECG	X	X	Day 5	X			X		Electrocardiogram (ECG) Can be done more frequently if clinically indicated (e.g., elevated troponin post baseline level) per safety cardiac monitoring (Section 10.5)
	X								If subjects are on telemetry, ECG is only required at screening.
Vital signs	X	X	X	X	X	X	X		Temperature should be collected twice per day (morning and night) while hospitalized; same method for temperature measurement should be used throughout the study
Chest x-ray or CT scan of lungs (if conducted as SOC)	X						X		Computed tomography (CT), standard of care (SOC) Same modality to be used throughout the study, where possible

Procedure	Screening	Treatment Period			Follow-up			Post-study visit	Notes
		BL	Daily visits [‡]	EOT/ET*			EOS		
Study Day	-3 to -1	1	2-9	10	14	21	28	+60 days from EOS	Baseline (BL); End of Treatment (EOT), Early termination (ET); End of study (EOS) ‡ If a subject is discharged prior to Day 10, they will complete Day 5 and Day 10 visits assessments * This visit will be conducted at hospital discharge, if subject is discharged prior to Day 10
Visit window (days)				±1	±2	±2	±2	±10	
SpO ₂ %	X	X	X	X	X	X	X		Peripheral capillary oxygen saturation (SpO ₂) is to be recorded morning and night while hospitalized (coinciding with body temperature)
Record FiO ₂	X	X	X	X	X	X	X		Fraction of inspired oxygen (FiO ₂) at each SpO ₂ assessment (morning and night while hospitalized)
FVC							*	X*	Forced vital capacity (FVC) *Subjects will be requested to conduct FVC post study, approximately 50 to 70 days after last follow-up visit
APACHE II score		X							APACHE (acute physiology and chronic health evaluation)

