10.3.1. Definition of AE

AE Definition

 • An AE is any untoward medical occurrence in a patient or clinical study subject, temporally associated with the use of study drug, whether or not considered related to the study drug. • NOTE: An AE can therefore be any unfavorable and unintended sign (including an abnormal laboratory finding), symptom, or disease (new or exacerbated) temporally associated with the use of study drug.

Events Meeting the AE Definition

 • Any abnormal laboratory test results (hematology, clinical chemistry, or urinalysis) or other safety assessments (e.g., ECG, radiological scans, vital signs measurements), including those that worsen from baseline (see bullet below), considered clinically significant in the medical and scientific judgment of the Investigator (i.e., not related to progression of underlying disease). • Exacerbation of a chronic or intermittent pre-existing condition including either an increase in frequency and/or intensity of the condition. • New conditions detected or diagnosed after study drug administration even though it may have been present before the start of the study. • Signs, symptoms, or the clinical sequelae of a suspected drug-drug interaction. • Signs, symptoms, or the clinical sequelae of a suspected overdose of either study drug or a concomitant medication. Overdose per se will not be reported as an AE/SAE unless it is an intentional overdose taken with possible suicidal/self-harming intent. Such overdoses should be reported regardless of sequelae.

Events NOT Meeting the AE Definition

 • Any clinically significant abnormal laboratory findings or other abnormal safety assessments which are associated with the underlying disease, unless judged by the Investigator to be more severe than expected for the subject's condition. • The disease/disorder being studied or expected progression, signs, or symptoms of the disease/disorder being studied, unless more severe than expected for the subject's condition.

- Medical or surgical procedure (e.g., endoscopy, appendectomy): the condition that leads to the procedure is the AE.
- Situations in which an untoward medical occurrence did not occur (social and/or convenience admission to a hospital).
- Anticipated day-to-day fluctuations of pre-existing disease(s) or condition(s) present or detected at the start of the study that do not worsen.

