1.1. Objectives and Endpoints

Objectives	Endpoints
Primary	

 To evaluate clinical benefit of BLD-2660 in hospitalized adults with recently diagnosed SARS-CoV-2 infection 	
 Time to recovery as defined by no longer requiring oxygen support or hospital discharge, whichever occurs first

 To evaluate improvement in oxygenation in hospitalized adults with COVID-19 treated with BLD-2660 	
 Change from baseline to Day 10 or hospital discharge, if sooner, in the ratio of peripheral hemoglobin oxygen saturation to fraction of inspired oxygen (SpO₂/FiO₂)
Secondary	

 To evaluate the safety and tolerability of BLD-2660 in the same population 	
 Incidence of TEAEs and serious adverse events (SAEs)

 To evaluate improvement in Biomarkers 	
 Change from baseline to Days 10/EOT, 14, 21 and 28 in serum calprotectin

 Additional efficacy outcomes 	
 Time to hospital discharge readiness Proportion of participants reporting each 6-point ordinal scale of the clinical status outcome assessment Change from baseline to Days 10/EOT, 14, 21 and 28 in IL-6 and D-dimer

Objectives	Endpoints
Exploratory	

 Other efficacy outcomes 	
 Proportion of participants who require mechanical ventilation after study entry

 To evaluate antiviral activity of BLD-2660 in the same population 	
 Change from baseline in SARS-CoV-2 viral load at Days 5, 10/EOT, 14, and 28

 Other safety outcomes 	
 Clinically relevant changes from baseline in electrocardiogram (ECG), and clinical laboratory values at each post baseline time point Proportion of participants with clinically significant drug-related troponin elevations that have repeat elevation upon confirmatory testing as adjudicated by the DMC while continuing study drug during the 10-day treatment period

 To assess population pharmacokinetics (PK) characteristics of BLD-2660 	
 BLD-2660 plasma concentrations

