5.8.4. Vital Sigs

Descriptive summary statistics of the observed values for blood pressure (systolic and diastolic), heart rate, temperature and respiratory rate data collected at screening, baseline and post-baseline visits will be presented by treatment group. As temperature is collected twice daily while a participant is hospitalized, the average of the daily measurements will be used. Boxplots will be

used to display the distribution of the observed values over time, using all post baseline assessments, by treatment group.

Participants with clinically significant values for any vital signs are to be reported as an AE and therefore clinically significant vital sign findings will be interpreted from the AE summaries.

5.8.5. 12-Lead ECG

Descriptive summary statistics of the observed values for 12-lead ECG data at screening, baseline and each post-baseline visit (i.e., Day 5/Discharge, Day 10/Discharge, 14, 21 and 28) will be presented by treatment group. Boxplots will be used to display the distribution of the observed values over time, by treatment group.

Participants with clinically significant values for any 12-lead ECG findings are to be reported as an AE and therefore clinically significant 12-lead ECG findings will be interpreted from the AE summaries.

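### Clinically significant laboratory and ECG changes are identified only through AE summaries, although the protocol's rules on recording them as AEs conflict; ECG change from baseline, part of a stated endpoint, is not summarised

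*SAP*

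**What the plan says.** Both documents list an exploratory safety endpoint, which the SAP (1.1) words as "Clinically relevant changes from baseline in electrocardiogram (ECG), and clinical laboratory values at each post baseline time point". Protocol section 3 has the same endpoint.

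For laboratories, SAP 5.8.3 plans "Descriptive summary statistics of the observed values and change from baseline values for hematology, chemistry and urinalysis data", by visit and arm, with boxplots of observed values. On clinical significance it says "Participants with clinically significant values for any safety labs are to be reported as an AE", and that therefore "clinically significant laboratory findings will be interpreted from the AE summaries". It adds one separate output: "A listing of participants with clinically significant drug-related troponin elevations that have repeat elevation upon confirmatory testing as adjudicated by the DMC".

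For ECG, SAP 5.8.5 plans "Descriptive summary statistics of the observed values for 12-lead ECG data", by visit and arm. Change from baseline is not mentioned. Clinically significant ECG findings are again left to the AE summaries.

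The protocol gives sites two instructions. Section 10.3.1 lists among events that do not meet the AE definition "Any clinically significant abnormal laboratory findings or other abnormal safety assessments which are associated with the underlying disease", with an exception where the investigator judges the finding more severe than expected for that subject. Section 8.2.4 tells the investigator to enter any clinically significant adverse laboratory change in the AE section of the eCRF.

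The Schedule of Activities (protocol 1.2) has a note in the ECG row: "If subjects are on telemetry, ECG is only required at screening".

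**The concern.** The SAP's reasoning is that clinically significant values become AEs, so the AE tables will show them. If sites follow protocol 10.3.1, that does not hold. In patients hospitalised with COVID-19, a site may attribute a change in liver enzymes, creatinine, platelets or ECG to the disease, and it then need not be recorded as an AE. A drug effect confined to a minority of subjects could be under-counted in the one place where the SAP looks for clinical significance.

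Two gaps do not depend on how sites report. The AE tables have no visit dimension, so even complete reporting could not show clinically relevant change at each time point. For ECG, the quantity named in the endpoint, change from baseline, is not produced.

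**Working it through.** No figure in the plan has to be reproduced. The check sets the passages against each other and then uses an assumed example to show what the planned outputs would reveal.

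**Passages side by side**

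1. *Premise against the AE rule.* SAP 5.8.3 and 5.8.5 assume that every clinically significant value is an AE. Protocol 10.3.1 excludes those associated with the disease, subject to its exception. The companion list of events that do meet the definition also explains clinical significance as meaning unrelated to disease progression.
2. *The competing instruction.* Protocol 8.2.4 supports the SAP's premise, but for laboratory tests only and not for ECG. Protocol 8.3 refers sites to Appendix 3 (10.3) for the AE definition. Two instructions are in force and sites may follow either.
3. *Precedence.* SAP section 1 says that the SAP prevails where the documents differ. That governs the analysis; it cannot restore events that sites did not record.
4. *Time dimension.* SAP 5.8.2 tabulates TEAEs by arm, system organ class and preferred term. The endpoint is defined at each post-baseline time point.
5. *ECG change.* Protocol 8.2.3 obtains PR, QRS and QT (QTcF). SAP 5.8.5 summarises observed values only.
6. *ECG visits.* SAP 5.8.5 lists Days 5, 10, 14, 21 and 28. The schedule shows no ECG on Day 14 or Day 21, and the telemetry note reduces the requirement to screening for monitored subjects. SAP 5.2 maps screening data to a missing baseline, so a baseline ECG would exist; it is post-baseline values that may be absent. The SAP does not plan to count them.
7. *Internal comparison.* SAP 5.8.6 tabulates abnormal, clinically significant physical findings by time point, with the safety set as denominator. Laboratories and ECG have no equivalent.

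**Assumed example (none of these rates is in the documents)**

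Suppose that, at one visit, 8 of the 80 active subjects rise from ALT 40 to 240 U/L, the other 72 do not change, and the ULN is 40.

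- Affected: 8/80 = 10%, each at 240/40 = 6 x ULN.
- Shift in arm mean: 8 x (240 - 40)/80 = 20 U/L.
- SD of change: 200 x sqrt(0.1 x 0.9) = 60 U/L, against 0 without these subjects.
- Maximum change: 200 U/L. Median and both quartiles: 0.
- AE table, if k of the 8 are attributed to COVID-19 and not recorded: (8 - k)/80. For k = 0 this is 10%; for k = 4, 5%; for k = 8, 0%.

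SAP 5.1 requires the SD and maximum, and SAP 5.3.2 keeps all values, so the planned numeric summaries would signal outliers. They would not give the number of subjects affected, or relate values to each local laboratory's limits. The AE table gives a count, but one that depends on k. Exclusion criterion 8 allows entry with ALT or AST up to 5 x ULN, so a high value after baseline is informative only when set against its own baseline.

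**The case against.** The strongest case on the other side is that this concerns one exploratory endpoint in a Phase 2 trial with descriptive safety analyses. Protocol 9.4.3 asks only for summaries by treatment and time point, which the SAP provides. Troponin, the only risk named in protocol 2.3.1, has its own adjudicated listing. Protocol 8.2.4 supports the SAP's premise for laboratories. Table and listing specifications are in a separate document that is not available here and may contain more. These points stand, and they limit the finding.

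A reader might go further than the documents allow in four ways:

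- *That the laboratory change-from-baseline endpoint is not delivered at all.* It is partly delivered: numeric change is planned by visit and arm. What is missing is participant-level clinical relevance.
- *That a drug effect would be visible only if a site declined to attribute it to COVID-19.* In the example above, the SD and maximum would show it.
- *That attribution by sites discards the placebo comparison.* Attribution is made blind under the same rules in both arms, and AE tables are presented by arm. Sensitivity may fall; bias is not shown.
- *That telemetry removes every post-screening ECG.* The note applies to subjects on telemetry. Its reach to later visits, such as Day 28 after discharge, is not stated. The schedule also allows additional ECGs when clinically indicated, and protocol 10.5 requires one in a troponin work-up.

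The objection does not answer two points: ECG change from baseline is absent, and 8.2.4 does not cover ECG.

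**Conclusion.** The point holds and should be corrected, but it does not threaten the trial. Apart from troponin, clinical significance of laboratory and ECG findings rests on AE summaries whose completeness depends on two conflicting protocol instructions. For ECG, the stated change-from-baseline endpoint is not summarised. For laboratories it is delivered numerically, but without a count of participants with clinically relevant change by time point.

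The effect is a loss of sensitivity that cannot be sized: neither document gives the proportion of abnormalities that sites would attribute to COVID-19, or how often the more-severe-than-expected exception would be used. The conclusion assumes that the unseen table specifications do not already supply the missing outputs; the SAP text gives no sign that they do.

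**What to change.** **SAP 5.8.5 (ECG).** Add change from baseline in QTcF, PR and QRS, and the number and proportion of participants with categorical QTcF increases, by arm and visit. Report by arm and visit the number without a 12-lead ECG because of telemetry.

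**SAP 5.8.3 (laboratories).** Add by-arm shift tables of baseline grade against worst post-baseline grade, and against grade at each visit. Use CTCAE v5, already the study's severity scale, or multiples of the local laboratory's ULN or LLN. Build the tables from recorded values, not from AE reports.

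**Reconcile.** Protocol 8.2.4 and 10.3.1 must be reconciled with each other and with SAP 5.8.3 and 5.8.5. The ECG schedule (telemetry note, no ECG on Day 14 or 21) must be reconciled with the visits listed in SAP 5.8.5. SAP 5.10 records that enrolment had already completed, so clarifying the recording rule cannot be relied on to recover AEs not entered. Tables from recorded values do not depend on it.

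**Cost.** SAP wording and a few standard tables before database lock, with no new subjects or procedures. Grading needs each local laboratory's reference ranges in the database, which is assumed and should be confirmed first.
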